#### **10.1.3 Month 4 (Visit 3)**

Upon arrival at the clinic on Visit 3 (month 4 ±30 days) the following assessments will be performed:

- Prior to the morning dose of ENVARSUS XR, patients will have approximately a 5 mL whole blood sample taken for tacrolimus trough measurement.
- Vital signs measurements.
- Patients will then be instructed to take their morning dose of ENVARSUS XR.
- QoL and cognitive tests will then be performed after the morning ENVARSUS XR dose including PGI-I, WHODAS, PIRS-20, and cognitive tests (in the same order as described above for Visit 2).

- CGI-I will be used to evaluate global change by the Investigator or designated back-up physician.
- Concomitant medication use (including evaluating compliance to immunosuppressive therapy) and AEs will be evaluated and recorded.
- Prior to leaving the clinic, all patients will be prescribed ENVARSUS XR for 4-month with refills with instructions to take the medication prior to noon each day for the remainder of the study. Patients will be reminded not to take their daily dose of ENVARSUS XR prior to their clinic at Visit 4 and to bring all remaining ENVARSUS XR medications to that visit.
- 

#### **10.1.4 Month 8 (Visit 4)**

Upon arrival at the clinic on Visit 4 (Month 8  $\pm$  30 days) same assessments as Visit3 will be performed:

- Prior to the morning dose of ENVARSUS XR, patients will have approximately a 5 mL whole blood sample taken for tacrolimus trough measurement.
- Vital signs measurements.
- Patients will then be instructed to take their morning dose of ENVARSUS XR.
- QoL and cognitive tests will then be performed after the morning ENVARSUS XR dose including PGI-I, WHODAS, PIRS-20, and cognitive tests (in the same order as described above for Visit 3).
- CGI-I will be used to evaluate global change by the Investigator or designated back-up physician.
- Concomitant medication use (including evaluating compliance to immunosuppressive therapy) and AEs will be evaluated and recorded.
- .
- All patients will be asked to bring ENVARSUS XR with them to be reviewed by the study nurse. The continuation of ENVARSUS XR will be at the discretion of the patient's treating nephrologist.

#### **10.1.5 Standard of Care (SOC) Study Visits**

At any time during the treatment period, an SOC study visit may be necessary for clinical cause, such as a sign or symptom of drug toxicity/intolerance, an AE, or a suspected acute rejection episode. A whole blood tacrolimus trough level should be recorded, if applicable, for patients for whom dose-adjustment of ENVARSUS XR is indicated.

#### **10.1.6 Early Withdrawal Study Visits**

An early-withdrawal visit should be scheduled as soon as possible for patients who withdraw from the study. Assessments of concomitant medication use, and AEs will be performed at this visit. .

Patients who withdraw from the study will not be replaced. Follow-up will occur for any ongoing AEs at the time of withdrawal. The Investigator will be responsible for informing IRBs of the early termination of the study.

#### 10.1.7 Permissible Visit Schedule Changes

Visit variations are allowed for logistic considerations and to accommodate scheduling conflicts. A +7-day window is permitted for scheduling visits.

**Table 10-1 Permissible Visit Schedule Changes**

|                                                                  |                                                                                                   |
|------------------------------------------------------------------|---------------------------------------------------------------------------------------------------|
| Screening: Day -30 to Day -1 (Visit 1)                    | Target date is 4 weeks to 10 years post-transplant, 1 to 30 days prior to enrollment date. |
| Enrollment: Day 0 (Visit 2)                               | Enrollment date                                                                            |
| Visit 3 (Month 4): Month 4 $\pm$ 30 days Window (Visit 3) | Target date $\pm$ 30 days
Target date is Enrollment (Visit 2) date + 4 months.          |
| Visit 4 (Month 8): Month 8 $\pm$ 30 days Window (Visit 4) | Target date $\pm$ 30 days
Target date is Enrollment (Visit 2) + 8 months.               |

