### **Study Visits:**

The study includes 4 scheduled visits (unless Visits 1 and 2 are combined). Visits should be scheduled to coincide with SOC visits, where possible. Withdrawal visits will be scheduled for all enrolled patients who terminate early prior to Visit 4. Visit times as well as follow up testing windows are “approximate.”

Visit 1 – Screening (Days -30 to -1): Patients will be confirmed to have had a minimum of 4 to 7 days on a stable dose of TAC-IR. Screening activities will include informed consent and eligibility review, including the Beck Depression Inventory (BDI-II).

Visit 2 – Enrollment/Baseline (Day 0): Patients will be confirmed to have had a stable dose of

TAC-IR (pre-conversion). This visit will include baseline cognitive assessments, a demographics survey, the WHODAS and PIRS-20. Patients will take their morning dose of TAC-IR and complete all of the baseline assessments; once completed, ENVARSUS XR will be prescribed and the first dose of ENVARSUS XR will be taken as soon as possible but no later than the next 30 days. (Patients who are unable to start ENVARSUS XR the next morning are to have the Visit 3 date adjusted accordingly).

Visit 1 and Visit 2 may be combined if no dose adjustments were performed and the patient has been maintained on a stable dose of tacrolimus with trough level between 3-9 ng/mL and the physician does not deem any dose adjustment required and Envarsus XR will be started as soon as possible but no later than the next 30 days

Note that the designation of Visit 2 as occurring on ‘Day 0’ is meant to reflect that ENVARSUS XR dosing is to start as soon as possible but no later than the next 30 days (Envarsus start day is the anchor point for subsequent visits).

Visit 3 (Month 4± 30 days): Patients will be confirmed to have been on a stable dose of once-daily ENVARSUS XR before Visit 3 assessments are performed. Patients will take their morning dose of ENVARSUS XR and complete the following activities: PGI-I, WHODAS, PIRS-20, and cognitive outcomes assessments (listed above under primary and secondary endpoints). The physician will perform CGI-I and prescribe a 4-month supply with refills of ENVARSUS XR.

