## 9.2 Study Drug Dosing and Administration

ENVARSUS XR tablets will be administered orally q.d. in the morning based on a conversion factor from tacrolimus to ENVARSUS XR of 1:0.8 (see [Appendix 2 or https://www.envarsusxr.com/hcp/professional-resources/envarsus-xr-dose-converter/](https://www.envarsusxr.com/hcp/professional-resources/envarsus-xr-dose-converter/) and [PI discretion](#)) to maintain target trough level of 3-9 ng/mL. The following dosing instructions should be observed:

- Patients should take ENVARSUS XR on an empty stomach at the same time of the day, preferably in the morning (to ensure consistent and maximum possible drug exposure).
- Patients should swallow ENVARSUS XR whole with fluid (preferably water) and should not chew, divide, or crush the tablets.
- If a dose is missed, the patient should take it as soon as possible within 14 hours after the scheduled time and inform the study investigator; beyond the 14-hour time frame, the patient should wait until the usual scheduled time to take the next regular daily dose.
- Patients should avoid eating grapefruit or drinking grapefruit juice or alcoholic beverages while taking ENVARSUS XR.

Patients should be encouraged to take their study treatment on a consistent schedule with regard to time of day and relation to meals except on their study visit days. Patients will be instructed not to take their morning dose of TAC-IR prior to their clinic visit (Visit 2) but to take their morning concomitant medications as they normally would. Once at the clinic at Visit 2, after the TAC-IR trough level blood sample has been drawn, the patient will take the morning dose of TAC-IR. ENVARSUS XR will be prescribed, and patients will be instructed to begin taking ENVARSUS XR the following morning.

Likewise, for Visit 3, patients will be instructed not to take their morning dose of ENVARSUS XR prior to their clinic visit (Visit 3), after the ENVARSUS XR trough level blood sample has been drawn, the patient will take the morning dose of ENVARSUS XR.

For Visit 4, patients will be instructed not to take ENVARSUS XR before coming to the clinic; after their ENVARSUS XR trough blood draw and other procedures for the visit, they will take their last single daily dose of ENVARSUS XR.

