## 10 STUDY VISITS AND ACTIVITIES

### 10.1 Study Activities by Visit

The specific study procedures to be performed at each visit are provided in the Schedule of Study Activities ([Table 3-1](#)). Permissible visit schedule changes are provided in [Section 10.1.7](#). Visits should be scheduled to coincide with SOC visits, where possible.

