#### 10.1.2 Enrollment (Visit 2)

Note that the designation of Visit 2 as occurring on 'Day 0' is meant to reflect that ENVARSUS XR dosing is to start as soon as possible but no later than the next 30 days. Visit 1 and Visit 2 may be combined if no dose adjustments were performed and the patient has been maintained on a

stable dose of TACIR with trough level between 3-9 ng/mL, and the physician does not deem any dose adjustment required.

Upon arrival at the clinic at Visit 2 the following assessments will be performed:

- Prior to the morning dose of TAC-IR, the patient will have approximately 5 mL of whole blood drawn for the assessment of TAC-IR trough.
- After confirmation of patient eligibility, a blood drawn for safety laboratory parameters (approximately 15 mL, for complete blood count [CBC] and a metabolic profile [blood glucose, calcium, sodium, potassium, CO2 (carbon dioxide, bicarbonate), chloride, blood urea nitrogen (BUN) and creatinine]).
- Physical examination and vital signs measurements.
- Patients will then be instructed to take their morning dose of TAC-IR.
- QoL and cognitive tests will then be performed after the morning TAC-IR dose in the following order:
  - WHODAS; ○ PIRS-20; ○ RBANS, ○ TMT-A and TMT-B;
  - After cognitive tests, ENVARSUS XR will be prescribed and patients will be instructed to take the first dose of ENVARSUS XR as soon as possible but no later than the next 30 days . Patients must be instructed to take their evening dose of TAC-IR.
- Concomitant medication use (including compliance to immunosuppressive therapy and adequate drug supply) and the safety monitoring processes will be initiated.
- Prior to leaving the clinic, the patient will be prescribed ENVARSUS XR with instructions to take the medication as soon as possible but no later than the next 30 days prior to noon each day for the remainder of the study. Patients will be reminded not to take their daily dose of ENVARSUS XR prior to their clinic at Visit 3 and to bring all remaining ENVARSUS XR medications to that visit.

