### **14.3 General Considerations**

#### **14.3.1 Definition of Study Days**

For the purpose of listing and summarizing data, time-in-study for each patient observation will be defined using study days. Study day is defined as the difference between the date of interest and the date of first dose of ENVARSUS XR. One day will be added if this difference is 0. The day prior to the first dose date is considered as “Study Day -1”. There is no “Study Day 0” for analysis purposes. In general, it is expected that enrollment date is the same date of the first dose date of ENVARSUS XR.

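### Table 10-1 times Visits 3 and 4 from Visit 2 and the synopsis times them from the first ENVARSUS XR dose; both can be met, but the table also accepts a Visit 3 at 60 to 89 days on drug, below the synopsis minimum of 90

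*Combined protocol and SAP*

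**What the plan says.** **Visit timing**

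- Section 10.1 directs staff to section 10.1.7: "Permissible visit schedule changes are provided in" that section. Table 10-1 there puts the Visit 3 target at "Enrollment (Visit 2) date + 4 months" and the Visit 4 target eight months after Visit 2, each ±30 days.
- The sentence above the table reads "A +7-day window is permitted for scheduling visits". It names no anchor.
- The synopsis (Study Visits) states "Envarsus start day is the anchor point for subsequent visits" and, for late starters, "Patients who are unable to start ENVARSUS XR the next morning are to have the Visit 3 date adjusted accordingly". It also uses ±30 days and describes visit times and windows as approximate.
- Section 10.1.2 allows the delay: "ENVARSUS XR dosing is to start as soon as possible but no later than the next 30 days".
- Section 14.3.2 analyses by nominal visit and applies no analysis window.

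**Sentences that fit only an immediate switch**

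- Section 9.2: "patients will be instructed to begin taking ENVARSUS XR the following morning".
- Section 14.3.1: "it is expected that enrollment date is the same date of the first dose date of ENVARSUS XR", worded as a general expectation.
- Section 6.1 (text under Figure 6-1): the last TAC-IR dose is taken on the evening of Visit 2, yet the same sentence repeats the 30-day allowance for starting ENVARSUS XR.

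**Order of dose and tests at Visit 4**

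- Section 9.2 places the dose after the trough sample and the visit's remaining procedures.
- The synopsis, section 6.1 and section 10.1.4 all place the morning dose before the quality-of-life and cognitive tests.

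**The concern.** The primary endpoint is the RBANS change from Visit 2 to Visit 3. If the start is late, the two anchors give different target dates, and no passage says which prevails. The synopsis shows the intention, but section 10 points staff to the table that carries the other rule. A coordinator scheduling from Table 10-1 can bring a late starter back with less time on ENVARSUS XR than the synopsis window allows. Because the analysis uses nominal visits, that record is pooled with the rest. The two rules can also disagree on whether a given visit date is a deviation.

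The linked sentences raise different issues. The TAC-IR sentence in 6.1, taken literally, leaves a kidney recipient without tacrolimus between the evening of Visit 2 and a delayed first dose. The Visit 4 sentence in 9.2, if followed, would make the Visit 4 tests pre-dose while those at Visits 2 and 3 are post-dose.

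**Working it through.** **Inputs.** Visit 3 at 4 months and Visit 4 at 8 months, each ±30 days (Table 10-1; synopsis). Start delay d = 0 to 30 days after Visit 2 (synopsis; 10.1.2). Assumption: 30-day months, so targets are 120 and 240 days. Let w be the offset from target, −30 to +30.

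**Formulas for Visit 3**

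- Days on drug, Table 10-1 anchor: 120 + w − d.
- Days on drug, synopsis anchor: 120 + w, so 90 to 150 at any delay.
- Days on drug common to both windows: a span of 60 − d days.

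| Start delay d | Table 10-1: on target | Table 10-1: window | Synopsis window | Common span | Accepted by the table but below 90 |
|---|---|---|---|---|---|
| 0 | 120 | 90–150 | 90–150 | 60 | none |
| 7 | 113 | 83–143 | 90–150 | 53 | 83–89 |
| 14 | 106 | 76–136 | 90–150 | 46 | 76–89 |
| 30 | 90 | 60–120 | 90–150 | 30 | 60–89 |

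**Can both rules be met?** The synopsis target falls at Visit 2 + 120 + d, which is at most 120 + 30 = 150 days after Visit 2. Table 10-1 accepts 90 to 150 days after Visit 2, so the synopsis target is always inside. For Visit 4 it is 240 + d, at most 270, against an accepted 210 to 270.

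**When does Table 10-1 leave the synopsis window on the short side?** When 120 + w − d < 90, that is, when days early (−w) plus start delay d exceeds 30. A visit on or after the Table 10-1 target never does this: with w = 0 and d = 30 the patient has 90 days on drug, the lower edge of the synopsis window. The 60-day minimum needs the full delay and the full 30 days early.

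**Visit 4.** With d = 30, Table 10-1 gives 210 days on target (180–240) against 240 (210–270).

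**Month length.** With 30.44-day months and d = 30, Visit 3 is at 91.8 against 121.8 days on target, and 61.8 against 91.8 at the early limit. The gap between the rules is unchanged, since it equals d.

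**The +7-day sentence.** Read with the table's own anchor, it allows Visit 3 only at 120 to 127 days after Visit 2; the table allows 90 to 150. The visit schedule, the synopsis and sections 10.1.3 and 10.1.4 all give ±30 days, so the +7-day sentence is the outlier.

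**Retest interval under the synopsis anchor.** Visit 2 to Visit 3 is (90 + d) to (150 + d) days, so at most 180, against at most 150 under Table 10-1.

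**The case against.** The strongest reply is that the mismatch forces no mistiming. A site can satisfy both rules at every permitted delay, and the synopsis has a specific instruction for late starters that would reasonably override a generic target date. Section 14.3.1 already counts study days from the first dose. All of this stands, and it is why the point is minor.

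A reader might infer that an on-target Visit 3 under Table 10-1 is too early because it can fall at 90 days instead of 120. The documents do not support that: 90 days is inside the synopsis window. A reader might also infer that section 10.1.7 as a whole sets a Visit 2 anchor. Only its table does.

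Nor do the documents show harm to the primary result. The package insert (section 2.5) puts steady state at about 7 days, so 60 days is well past it. Section 9.3 accepts Visit 3 testing after 4 days on a stable dose following an adjustment. The study is exploratory, and section 14.6.1 already summarizes exposure up to each visit. What remains is that this summary would reveal short exposure only after the visit had taken place.

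On Visit 4, section 9.2 names no test, and section 10.1.4 puts vital signs between the trough sample and the dose, so the sentence could mean only that. But the Visit 3 sentence in the same section puts the dose straight after the trough sample. Against that contrast, the natural reading of the Visit 4 sentence is that the dose comes last.

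**Conclusion.** The inconsistency is real, sits in current text, and is minor. Its practical size is the set of Visit 3 dates at 60 to 89 days on drug that Table 10-1 accepts and the synopsis does not, reached only when start delay plus days early exceeds 30. This assumes 30-day months and takes the windows at face value, although the synopsis calls them approximate. The documents give no distribution of start delays, so the number of patients affected cannot be estimated. No RBANS effect can be derived; it is probably small.

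The +7-day sentence contradicts the table beneath it. The TAC-IR sentence in 6.1 needs correcting because its literal reading, surely unintended, leaves a tacrolimus gap. The Visit 4 order concerns Visit 4 data only: the primary endpoint and the listed cognitive endpoints end at Visit 3, and the one efficacy endpoint that uses Visit 4 is the WHODAS change.

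**What to change.** 1. Table 10-1: set the Visit 3 and Visit 4 targets at the first ENVARSUS XR dose + 4 and + 8 months, ±30 days, as the synopsis already intends.
2. Section 10.1.7: delete the +7-day sentence.
3. Section 6.1: state that TAC-IR continues until ENVARSUS XR is started.
4. Sections 9.2 and 14.3.1: align the next-morning start and the same-date expectation with the 30-day start rule.
5. Section 9.2, Visit 4: trough draw, then dose, then tests.

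The cost is wording in five places (9.2 twice, 6.1, 10.1.7 with its table, 14.3.1). No new data are needed, because the ENVARSUS XR start date is already captured (visit schedule, footnote a), and no analysis is added. The downside is a Visit 2 to Visit 3 interval of up to 180 days. The synopsis rule already implies this, and the RBANS has parallel forms for repeat testing (section 10.2.2.5).

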## 10.2 Study Assessments

This section provides the assessments to be performed in the study. The case report forms will be developed in REDCap.

### 10.2.1 Screening Assessment: Beck Depression Inventory (BDI-II)

The BDI-II is a widely used 21-item, self-report instrument that measures severity of depression in adults and adolescents in clinical and nonclinical settings. Each item is a list of four statements arranged in increasing severity about a particular symptom of depression. Scores for each item range from 0 to 3. The total BDI-II score is the sum of all responses, ranging from 0 to 63. Cut score guidelines for patients diagnosed with major depression are as follows: minimal (0-13), mild (14-19), moderate (20-28), and severe (29-63). The recall period of the BDI-II is the past two weeks, including today.

The BDI-II will be administered at the Screening Visit. Patients with a score of  $\geq 20$  (corresponding to moderate depression) will be excluded from the study. Administration time: approximately 5-10 minutes.

### 10.2.2 Baseline and Post-Baseline Assessments

The clinician should begin each study visit with the clinical assessments as specified in [Table 3](#), with the exception of Visit 3, where the clinical assessments are preceded by administration of the PGI-I. Following the clinical assessments, the corresponding assessments will be administered in the order specified in the following subsections, as per the schedule of assessments in [Table 3](#). Each visit will conclude with an assessment of adverse events for safety reporting and, if

applicable, dispensing of study drug, completion of the dose administration record, and study drug reconciliation (in that order).

#### **10.2.2.1 Demographics Survey**

The Demographics Survey provides overall demographic background on the patient population; survey is completed at Visit 2 at the same time when collecting demographics.

#### **10.2.2.2 Patient Global Impression of Improvement (PGI-I)**

The PGI-I measures change since initiating a medication and is assessed on a 7-point Likert-type scale ranging from very much better (1) to very much worse (7). The PGI-I will be administered at Visit 3 prior to other patient-reported outcomes (PRO) measures and clinical assessments. The PGI-I should be completed by the patient without input from clinical staff or friends or family members. Administration time: approximately 1 minute.

#### **10.2.2.3 World Health Organization Disability Assessment Schedule 2.0 (WHODAS)**

The 12-item WHODAS 2.0 includes 12 items assessing 6 disability domains in 2 components. The component “activities” includes cognition (learning and concentration), mobility (standing and walking) and self-care (washing and dressing oneself), and the component “participation” includes getting along (dealing with strangers and maintaining friendships), life activities (doing housework and working ability), and social participation (emotional functions and engaging in community). Each of the 12 items is rated according to a 5-point Likert-type scale, which grades the difficulty experienced by the participant in performing a given activity. The scoring is from 0 to 4, where 0 means no (0–4%), 1 means mild (5–24%), 2 means moderate (25–49%), 3 means severe (50–95%), and 4 means extreme or complete (96–100%) difficulty in this specific activity. The total score of WHODAS is the sum of all these 12 sub-scores and ranges from 0 to 48, with lower scores indicating better functioning. Total scores of 1–4 belong to mild disability, 5–9 to moderate disability, and 10–48 to severe disability (<http://www.who.int/classifications/ICF/who/whodasii/en/>).

The WHODAS will be administered at Visit 2, Visit 3, and Visit 4 in this study

